**Pharmacokinetics**

- EVG concentrations in:
  - Blood
  - Rectal fluid
  - Rectal mucosal tissue homogenates

- TAF and TFV concentrations in
  - Blood
  - Rectal fluid
  - **Rectal mucosal tissue homogenates**
- TFV-DP concentration in:
  - ~~◦ Rectal mucosal tissue homogenates~~
  - Rectal mucosal tissue cell isolates
- ~~• TFV concentrations in~~
  - ~~◦ Rectal mucosal tissue homogenates~~

2. In the second to fourth bullets of pharmacokinetics in the “Primary Endpoints” subsection of Section 4.2, *Summary of Major Endpoints*:

**Pharmacokinetics**

- EVG concentrations in:
  - Blood
  - Rectal fluid
  - Rectal mucosal tissue homogenates
- TAF and TFV concentrations in
  - Blood
  - Rectal fluid
  - **Rectal mucosal tissue homogenates**
- TFV-DP concentration in:
  - ~~◦ Rectal mucosal tissue homogenates~~
  - Rectal mucosal tissue cell isolates
- ~~• TFV concentrations in~~
  - ~~◦ Rectal mucosal tissue homogenates~~

3. In the second to fourth bullets of pharmacokinetics in the “Primary Endpoints” subsection of Section 10.2, *Study Endpoints*:

**Pharmacokinetics**

- EVG concentrations in:
  - Blood
  - Rectal fluid
  - Rectal mucosal tissue homogenates
- TAF and TFV concentrations in
  - Blood
  - Rectal fluid
  - **Rectal mucosal tissue homogenates**
- TFV-DP concentration in:
  - ~~◦ Rectal mucosal tissue homogenates~~
  - Rectal mucosal tissue cell isolates

- ~~TFV concentrations in~~
- ~~Rectal mucosal tissue homogenates~~

4. In the “Rectal Tissue” column in *Table 16: Specimens to be Collected to Assess Safety, PK and Ex Vivo Antiviral Activity*, of Section 7.10, *Pharmacokinetics (PK) and Pharmacodynamics (PD)*:

Study Visit	Specimens collected for PK, PD and mucosal safety			
	Blood	Rectal Fluid	Rectal Tissue	CVF
Visit 3 & Visit 7 - Samples collected at 1, 2, 4 and 6 hours	
 
• Blood for PK
 
	
Group 1 at 2-hour
 
 
• RF for microbiome
 
• RF for PK
 
• RF for PD
 
 
Group 1 at 6-hour
 
 
• RF for PK
 
 
Group 2 at 4-hour
 
 
• RF for PK
 
	
Group 1 only at 2-hour
 
 
• 7 samples for biomarkers
 
• 4 samples for PD
 
• 11 samples for PK               
 
○ 1 for EVG
 
○ 1 for TAF and TFV and <del>TFV- DP</del>
 
○ 1 for backup
 
○ 8 for MMC isolation
 
 
 
	
Group 1 at 2-hour
 
 
• CVF for microflora
 
• CVF for PK
 
• CVF for PD
 
 
Group 1 at 6-hour
 
 
• CVF for PK
 
 
Group 2 at 4-hour
 
 
• CVF for PK
 

5. Protocol Signature Page was updated to include Letter of Amendment #04; it is appended to the end of this document.

The above information, as well as the changes from LoA#01, LoA#02 and LoA#03, will be incorporated into the next version of the protocol at a later time if it is amended.

## 1. LIST OF ABBREVIATIONS AND ACRONYMS

A list of abbreviations used in the SAP.

Term/Abbreviation	Definition
AE	adverse event
ALT	Alanine aminotransferase
AST	Aspartate aminotransferase
%AUC ex	Percentage of AUC 0-∞ obtained by extrapolation, calculated as $[(C_{last} / k_e) / AUC_{0-∞} * 100]$
AUC	area under the concentration-time curve
AUC 0-t	AUC from time zero to the time of the last measurable concentration
AUC 0-∞	AUC from time zero extrapolated to infinity, equal to AUC 0-t plus AUC t-∞ = $(C_{last} / k_e)$
BMI	body mass index
BLOQ	below the limit of quantitation
CASI	computer assisted self-interviews
C last	last observed concentration
C max	peak concentration
CRS	Clinical Research Site
EVG	elvitegravir
h	hour
k e	terminal elimination rate constant
LLOQ	lower limit of quantification
MedDRA	Medical Dictionary for Regulatory Activities
PK	pharmacokinetics
RF	rectal fluid
RT	rectal mucosal tissue
SAP	statistical analysis plan
SSP	study specific procedures
t 1/2	terminal concentration half-life
TAF	tenofovir alafenamide
T max	time to peak concentration

## 2. INTRODUCTION

[figure not shown]
This Statistical Analysis Plan (SAP) describes the plan for the final analysis of data regarding the safety, pharmacokinetics, and acceptability among HIV-uninfected individuals 18 years of age or older in a Phase I, multi-site, open-label, single arm, two-period study of rectal administration of one Tenofovir Alafenamide/Elvitegravir Insert, 20/16 mg, and then two TAF/EVG Inserts.

### 2.1 General Design Considerations

#### PROTOCOL SUMMARY

Short Title:	Safety and PK Study of TAF/EVG Administered Rectally
Clinical Phase:	Phase 1
IND Sponsor:	DAIDS
Protocol Chair:	[name], MPH
Sample Size:	MTN-039 will enroll approximately 20 participants.
Study Population:	HIV-uninfected individuals 18 years of age or older
Study Sites:	Alabama CRS and University of Pittsburgh CRS
Study Design:	Phase 1, multi-site, open-label, single arm, two-period study of rectal administration of one Tenofovir Alafenamide/Elvitegravir Insert, 20/16 mg and then two TAF/EVG Inserts
Study Duration:	Approximately 6-13 weeks of follow-up per participant is planned with a projected accrual period of 6-8 months. The total duration of the study will be approximately 11 months.
Study Products:	TAF/EVG Insert, 20/16 mg
Study Regimen:	Participants will apply a single TAF/EVG Insert rectally and samples will be collected over a 3-day period. After a washout period of at least 7 days, participants will apply two TAF/EVG Inserts rectally and samples will be taken over a 3-day period.

**Figure 1: MTN-039 Study Visit Schedule**

As displayed in Figure 1, participants will receive a rectally administered dose of one TAF/EVG insert at Visit 3 and have safety laboratory tests, PK and PD assessments performed over the next three days (Visits 4, 5, and 6). Participants will self-administer a saline enema at home the evening prior to a clinic dosing visit (Visits 3 and 7). After a washout period of one to seven weeks following the last tissue sampling associated with one TAF/EVG insert dosing, participants will receive dosing of two TAF/EVG inserts at Visit 7 and have safety laboratory tests, PK and PD assessments performed over the next three days (Visits 8, 9, and 10). A final study contact will occur approximately 3-7 days after Visit 10 and may be conducted over the phone.

## 2.2 Study Objectives and Endpoints

The primary, secondary and exploratory objectives and endpoints of this study are described below. This SAP will describe the plan for the statistical analyses of the primary and secondary endpoints only.

### Primary Objectives:

#### Safety

- To evaluate the safety of the TAF/EVG Insert, 20/16 mg administered rectally at two dose levels: 1 insert and 2 inserts

#### Pharmacokinetics

- To characterize the systemic and rectal pharmacokinetics of the TAF/EVG Insert, 20/16 mg applied rectally at two dose levels: 1 insert and 2 inserts

### Primary Endpoints:

#### Safety

- All Grade 2 and higher AEs

#### Pharmacokinetics

- EVG concentrations in:
  - Blood
  - Rectal fluid
  - Rectal mucosal tissue homogenates
- TAF and TFV concentrations in
  - Blood

- Rectal fluid
- Rectal mucosal tissue homogenates
  
- TFV-DP concentration in:
  - Rectal mucosal tissue cell isolates

**Secondary Objective:**

**Acceptability**

- To identify product attributes considered likely to challenge and/or facilitate future sustained use of the TAF/EVG Insert applied rectally

**Secondary Endpoints:**

**Acceptability**

- Participant report of overall acceptability of the TAF/EVG Insert applied rectally

**Exploratory Objectives:**

**Ex Vivo Efficacy**

- To assess the preliminary (ex vivo) efficacy of TAF/EVG after product is inserted rectally

**Pharmacokinetics**

- To characterize the cervicovaginal pharmacokinetics of the TAF/EVG Insert, 20/16 mg applied rectally at two dose levels: 1 insert and 2 inserts

**Mucosal Safety**

- To evaluate mucosal safety of the TAF/EVG Insert, 20/16 mg applied rectally at two dose levels: 1 insert and 2 inserts

**Exploratory Endpoints:**

**Ex Vivo Efficacy**

- Changes in HIV-1 replication in colorectal explant culture supernatant
- Anti-HIV activity in rectal fluid
- Anti-HIV activity in cervicovaginal fluid

**Pharmacokinetics**

- EVG, TAF and TFV concentrations in cervicovaginal fluid

**Mucosal Safety**

- Rectal histology
- Rectal proteomics
- Rectal metabolomics
- Rectal immunophenotype
- Rectal microbiome
- Cervicovaginal microflora

**2.3 Randomization**

There will be no randomization to dose of TAF and EVG (one or two inserts) in this open-label, single arm, and two-period trial.

At study randomization upon enrollment, participants will be assigned to one of two sampling group schedules for collection of rectal tissue (collected with flexible sigmoidoscopy), rectal fluid, and cervicovaginal fluid (if applicable):

Group 1: Visits 3, 5, 7, and 9

Group 2: Visits 4, 6, 8, and 10

Notes: Both sampling groups 1 and 2 will provide blood at Visits 3-10. At Visits 3 and 7, both sampling groups will provide rectal fluid and cervicovaginal fluid (if applicable) – Group 1 at 2- and 6-hours post-dose, and Group 2 at 4-hours post-dose. At Visits 3 and 7, rectal tissue sampling will be conducted in Group 1 participants at 2-hours post-dose. All sampling times are approximate; allowable windows and detailed instructions are provided in the MTN-039 SSP Manual.

Each participant will have a total of 5 flexible sigmoidoscopies for rectal tissue sampling:

- at baseline (both sampling groups, 1 set of biopsies)
- at 2- and 48-hours post-dose for each dose (Group 1 only, 4 sets of biopsies)
- at 24- and 72-hours post-dose for each dose (Group 2 only, 4 sets of biopsies).

Randomization will be stratified by sex at birth to incorporate at least three participants assigned female sex at birth in each sampling group.

## **2.4 Blinding**

There is no blinding in this open-label study.

## **2.5 Sample Size and Power**

The study is designed for a total accrual of twenty (20) participants, which gives sufficient power for the detection of adverse events as described in the protocol. Descriptive safety analyses and pharmacokinetic analyses are planned with no formal statistical testing.

# **3. GENERAL DATA ANALYSIS CONSIDERATIONS**

## **3.1 Analysis Set(s)**

The analysis set consists of all participants enrolled in the study who are administered a TAF/EVG insert at any dosing visit (Visit 3 or 7). All available safety, PK, and acceptability data will be analyzed on this set of participants, as described below.

## **3.2 Statistical Analysis Issues**

For the primary safety analyses, safety endpoints will be classified into groups by dose regimen (one or two inserts) based on the doses administered at a dosing visit (Visit 3 and 7). If a participant was not administered a particular dose, then the participant will be excluded from analyses describing that particular dose regimen.

For the primary pharmacokinetics analyses, timing of drug concentration results will be based on the time the specimen was actually collected, and not based on time points as planned for each sampling group

per randomization. Time points may still be grouped into categories based the average or targeted time point for specimen collection. The handling of missing data and concentration data below the limit of quantitation (BLOQ) are described in the section on pharmacokinetic analyses below.

#### **4. INTERIM ANALYSIS AND DATA MONITORING COMMITTEE**

No interim statistical analysis was planned or performed for the MTN-039 study.

One study monitoring committee (SMC) review was conducted for MTN-039, on December 7, 2020, for which a closed report was produced. Evaluation of safety was based on descriptive tables of adverse events, with no formal statistical testing.

#### **5. GENERAL ANALYSIS METHODS**

When the use of descriptive statistics to assess dosing regimen characteristics or differences is required, the following methods will be used: for categorical variables, the number and percent in each category; for continuous variables, the mean, median, standard deviation, quartiles, and range (minimum, maximum). Within-treatment group assessment of the change from the baseline measurement to a follow-up measurement will be analyzed using McNemar's test (for categorical response variables) or the paired t-test or Wilcoxon signed-ranks test (for continuous variables).

The following descriptions may be used to distinguish the dosing regimens: "One Insert" and "Two Inserts".

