### **Mucosal Safety**

- To evaluate mucosal safety of the TAF/EVG Insert, 20/16 mg applied rectally at two dose levels: 1 insert and 2 inserts

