**Table 12: Dosing Procedures**

Dosing Procedures – Visits 3 and 7	
Component	Procedures

Administrative and Regulatory		
 
Review/update locator information
 
Provide reimbursement
 
Schedule next visit/contact
 

Behavioral/Counseling		
 
HIV pre- and post-test counseling*
 
HIV/STI risk reduction counseling*
 
Protocol counseling
 

Clinical		
 
Review/update medical history
 
Review/update concomitant medications
 
Perform targeted physical examination*
 
Perform genital examination*
 
Perform pelvic examination* ▲
 
Perform rectal examination
 
Treat or prescribe treatment for RTI/UTI, or STIs*
 
Provide available test results
 
Collect/update AEs
 

Laboratory	Pharyngeal	
 
NAAT for GC/CT*
 

	Urine	
 
NAAT for GC/CT* ▼
 
Urine dipstick/culture*
 
Pregnancy test* ■
 

	Blood	
 
CBC with differential and platelets*
 
Chemistries (AST/ALT/creatinine)*
 
Syphilis serology*
 
HIV-1/2 test*
 
Blood for PK ◆
 

	Pelvic▲	
 
CVF for PK **
 
CVF for PD ♣
 
CVF for microflora ♣
 
NAAT for GC/CT/TV*
 

	Anorectal	
 
Rectal fluid for PK **
 
Rectal fluid for PD ♣
 
Rectal fluid microbiome ♣
 
Rectal tissue for PK ♣
 
Rectal tissue for PD ♣
 
Rectal tissue for biomarkers ♣
 
NAAT for GC/CT*
 

Study Product/Supplies		
 
Administration of study product
 
Offer condoms
 
Offer lubricant
 

\* If indicated ▲ Participants assigned female sex at birth and if anatomy allows ▼ If pelvic GC/CT cannot be performed ■ Participants of childbearing potential

◆ All participants will have blood collected at 1, 2, 4, and 6 hours following product administration.

♣ Group 1 only at 2 hours post-dose

\*\* Group 1: 2 and 6 hours post-dose; Group 2: 4 hours post-dose

## 7.4.2 Post-Dosing Visits – Visits 4 and 8

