**Table 13: 24-hour Post-Dosing Visits**

24-Hour Post-Dosing Visits - Visits 4 and 8		
Component	Procedures	
Administrative and Regulatory	
 
Review/update locator information
 
Provide reimbursement
 
Schedule next visit/contact
 
	
Behavioral/Counseling	
 
HIV pre- and post-test counseling*
 
HIV/STI risk reduction counseling*
 
Protocol counseling
 
Behavioral assessment (Brief CASI)
 
	
Clinical	
 
Review/update medical history
 
Review/update concomitant medications
 
Perform targeted physical examination*
 
Perform genital examination*
 
Perform pelvic examination* ▲
 
Perform rectal examination
 
Treat or prescribe treatment for RTI/UTI, or STIs*
 
Provide available test results
 
Collect/update AEs
 
	
Laboratory	Pharyngeal	
 
NAAT for GC/CT*
 

	Urine	
 
NAAT for GC/CT* ▼
 
Urine dipstick/culture*
 
Pregnancy test* ■
 

	Blood	
 
CBC with differential and platelets*
 
Chemistries (AST/ALT/creatinine)*
 
Syphilis serology*
 
HIV-1/2 test*
 
Blood for PK
 

	Pelvic▲	
 
CVF for PK ☼
 
CVF for PD ☼
 
CVF for microflora ☼
 
NAAT for GC/CT/TV*
 

	Anorectal	
 
Rectal fluid for PK ☼
 
Rectal fluid for PD ☼
 
Rectal fluid for microbiome ☼
 
Rectal tissue for PK ☼
 
Rectal tissue for PD ☼
 
Rectal tissue for biomarkers ☼
 
NAAT for GC/CT*
 

Study Product/Supplies		
 
Offer condoms
 

\* If indicated ▲ Participants assigned female sex at birth and if anatomy allows ▼ If pelvic GC/CT cannot be performed ■ Participants of childbearing potential ☼ Group 2 only

### 7.4.3 Other Post-Dosing Visits – Visits 5, 6, 9, and 10

The 48-hour Post-Dosing Visits (Visits 5 and 9) should occur between 44 and 52 hours (+/- 4 hours) after each dosing visit. The 72-hour Post-Dosing Visits (Visits 6 and 10) should occur between 66 and 78 hours (+/- 6 hours) after each dosing visit.

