## 10.5 Randomization Procedures

There will be no randomization to dose of TAF and EVG (one insert or two inserts) in this open-label, single-arm, and two-period trial. However, upon enrollment, participants will be randomly assigned to one of two sample collection schedules for the collection of rectal tissue (collected with flexible sigmoidoscopy), rectal fluid, and cervicovaginal fluid (if applicable):

Group 1: Visits 3, 5, 7, and 9

Group 2: Visits 4, 6, 8, and 10

Note: Both groups 1 and 2 will provide blood at Visits 3-10. At Visits 3 and 7, both groups will provide rectal fluid and cervicovaginal fluid (if applicable) – Group 1 at 2 and 6 hours post-dose, and Group 2 at 4 hours post-dose.

Randomization will be stratified by sex at birth to incorporate at least three participants assigned female sex at birth in each group.

The randomization scheme will be generated and maintained by the MTN SDMC.

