### 10.7.2 Primary Analysis

When the use of descriptive statistics to assess group characteristics or differences is required, the following methods will be used: for categorical variables, the number and percent in each category; for continuous variables, the mean, median, standard deviation, quartiles and range (minimum, maximum). Within-treatment group assessment of the change from the baseline measurement to a follow-up measurement will be analyzed using McNemar's test (for categorical response variables) or the paired t-test or Wilcoxon signed-ranks test (for continuous variables).

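### Change from baseline is given significance tests with no estimate or interval, SAP 2.5 says there is no formal testing, and at about 10 participants per biopsy time point a non-significant result could not be read as absence of harm

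*SAP*

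**What the plan says.** Two current passages prescribe tests for change from baseline. SAP 5 (General Analysis Methods) has "Within-treatment group assessment of the change from the baseline measurement to a follow-up measurement will be analyzed using McNemar's test (for categorical response variables", and continues with the paired t-test or Wilcoxon test for continuous measures. Protocol 10.7.2 (Primary Analysis) has the matching sentence: such changes "will be analyzed using McNemar's test (for categorical response variables) or the paired t-test or Wilcoxon signed-ranks test (for continuous variables". Neither gives a significance level, the version of McNemar's test, a relevant size of change, or an estimate with an interval.

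SAP 2.5 points the other way: "Descriptive safety analyses and pharmacokinetic analyses are planned with no formal statistical testing".

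Three further provisions decide where this matters:

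- SAP 2.2 limits the SAP to the primary and secondary endpoints.
- SAP 8.3 tabulates hematology and chemistries with descriptive statistics only.
- The protocol has an exploratory objective "To evaluate mucosal safety of the TAF/EVG Insert, 20/16 mg applied rectally at two dose levels: 1 insert and 2 inserts" (section 3.3). Its endpoints include rectal histology, proteomics, metabolomics, immunophenotype and microbiome. Protocol 10.7.3 covers acceptability, cervicovaginal PK, explant virus levels and anti-HIV activity in fluids. It names no analysis for mucosal safety.

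**The concern.** An analyst following SAP 5 would produce p-values. One following SAP 2.5 would not. That needs settling before the final analysis.

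The larger issue is what the protocol leaves for mucosal safety. The biopsies have an Enrollment baseline and post-dose follow-up, which is the structure the 10.7.2 sentence describes, and no other method is stated for them. If that sentence is applied, the result is a p-value from a very small paired sample, with no statement of how large a change the data leave open. In the first study of this insert given rectally, the useful question about mucosal change is how much harm can be excluded. A bare test does not answer it.

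**Working it through.** **Inputs**

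- Total sample size, SAP 2.5: "The study is designed for a total accrual of twenty (20) participants".
- Allocation, protocol 10.5: "participants will be randomly assigned to one of two sample collection schedules for the collection of rectal tissue". No ratio is given, so 10 per group is an assumption.
- Post-dose biomarker biopsies, Group 1: "Group 1 only at 2 hours post-dose" (protocol Table 12). Group 2: the line "Rectal tissue for biomarkers" in protocol Table 13 (24-hour visits) is marked for Group 2 only. Protocol Table 16 agrees, and lists no biomarker biopsies at 48 or 72 hours. So n is about 10 per dose and time point.
- Assumed, because the documents do not say: two-sided 0.05, no missing data, and the effect sizes below.

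**The plan's own figures**

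- Protocol Table 17, 5% event rate: 1 − 0.95^20 = 0.6415, against the stated 64.2% (0.64 in the text).
- Protocol Table 18, 0/20: upper bound 1 − 0.025^(1/20) = 16.8%, as stated.

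Both reproduce. They concern safety event rates. No operating characteristic is given for the change-from-baseline tests.

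**Paired t-test**

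Power comes from the noncentral t distribution with n − 1 degrees of freedom and noncentrality d√n, where d is the mean change in SDs of the paired differences. For n = 10 and d = 0.5, the noncentrality is 0.5 × √10 = 1.58, the critical value is 2.262, and power is 29.3%.

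| True shift | Miss rate, n = 10 | Miss rate, n = 20 |
|---|---|---|
| 0.3 SD | 86.4% | 75.3% |
| 0.5 SD | 70.7% | 43.5% |
| 0.8 SD | 38.4% | 7.6% |
| 1.0 SD | 19.7% | 1.1% |

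By simulation, the Wilcoxon test at n = 10 and 0.5 SD misses 72.1%. For 80% power the t-test needs a shift of about 1.0 SD at n = 10, or 0.66 SD at n = 20.

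**McNemar's test, all changes in one direction**

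The exact two-sided p-value for k one-way changes is 2 × 0.5^k. Five changes give 0.0625 and six give 0.031, so six are needed. With n = 10 and a true new-abnormality rate of 30%, power is P(Bin(10, 0.3) ≥ 6) = 4.7%.

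| True rate of new abnormality | Miss rate, exact test, n = 10 |
|---|---|
| 30% | 95.3% |
| 40% | 83.4% |
| 50% | 62.3% |

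The version matters. At a 30% rate, mid-p misses 85.0% and the uncorrected chi-square misses 65.0%; the continuity-corrected test behaves like the exact one. At n = 20 the exact test misses a 30% rate 41.6% of the time.

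**What an interval would show at n = 10**

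- Mean paired change: half-width 2.262/√10 = 0.72 SD.
- 0/10 newly abnormal: upper 95% bound 1 − 0.025^(1/10) = 30.8%.
- 5/10 newly abnormal: 18.7% to 81.3%, although the exact test on the same data gives p = 0.0625 if none reverse.

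**The case against.** The strongest reply is that the sentence is generic text attached to no named output. Within the SAP, adverse events get Clopper-Pearson intervals (8.1), laboratory values get descriptive tables (8.3), concentrations get means or medians with 95% intervals (9.2), and acceptability gets a summary table (10.1). On that view the clash between SAP 2.5 and SAP 5 is editorial. Much of this stands, and it limits the point in four ways.

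- A reader might infer that SAP 5 governs mucosal safety. It does not: SAP 2.2 excludes exploratory endpoints. The link runs only through protocol 10.7.2, which does not name those endpoints. Protocol 10.7.3 does not point back to the tests, although it refers back to the descriptive statistics for cervicovaginal PK. One could fairly say that mucosal safety has no stated analysis at all.
- A reader might include CBC and chemistries. SAP 8.3 handles these descriptively. They are also not split by sampling group, so about 20 participants contribute at Visit 10.
- A reader might treat a miss rate of 71% to 95% as a property of the plan. It holds only for a 0.5 SD shift (t-test) and a 30% rate (exact or continuity-corrected McNemar), at n = 10 and two-sided 0.05. The documents define no relevant harm and choose none of these settings.
- A reader might infer that non-significance will be taken as proof of safety. No passage says so.

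Protocol 10.7.2 also says formal comparisons will not be done, but that concerns the two doses. It neither resolves nor worsens the conflict over baseline tests.

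**Conclusion.** The point holds within those limits. SAP 5 and protocol 10.7.2 prescribe tests for within-regimen change with no estimate or interval, and SAP 2.5 says there is no formal testing; these passages need reconciling. The practical effect falls on the protocol's exploratory baseline-to-follow-up measures, chiefly the mucosal biomarkers.

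The size depends on the assumptions stated above. Across the effects considered at n = 10, the paired t-test misses between about 86% (0.3 SD) and 20% (1.0 SD), and exact McNemar between about 95% (30% rate) and 62% (50% rate). One result needs no assumed effect size: half of ten participants newly abnormal, with none reversing, is not significant by the exact test at 0.05. A non-significant result at these numbers could therefore not be read as absence of harm.

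This is a worthwhile, cheap improvement. The primary adverse-event analysis, with its exact intervals, is sound and unaffected.

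**What to change.** In protocol 10.7.2 and SAP 5, replace the test sentence with:

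> Within-regimen change from baseline will be reported by sampling time point as the mean paired difference with 95% CI (or Hodges-Lehmann estimate with CI) for continuous measures and, for categorical measures, as the number and proportion newly abnormal among those normal at baseline with Clopper-Pearson 95% CI, together with the number reverting to normal. Any p-values are descriptive and will not be used to conclude absence of harm.

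This brings SAP 5 into line with SAP 2.5 and extends interval methods the SAP already uses in 8.1 and 9.2. Because SAP 2.2 leaves mucosal safety out, the protocol wording is what carries the change for those endpoints; a cross-reference from protocol 10.7.3 would remove doubt that it applies. Each categorical measure also needs a written definition of abnormal.

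The cost is wording and minor programming, with no extra participants or samples. The downside is that intervals this wide will look less reassuring than a non-significant p-value.
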